6.2 Materials and Supplies

Treatment drugs (Investigational drug and Control) will be pre-randomized and blinded before arriving at each investigational site. A drug dispensing log will be kept current and will contain the following information:

- The identification of the subject to whom the drug was dispensed
- The date, quantity, and lot number of the drug dispensed to the subject

Drug inventory and accountability records (Test Article Accountability Log) will be maintained at each site. A monitor or designated site staff will reconcile drug inventory and review accountability records. Any unused vials of cetirizine will be returned to the sponsor or destructed on site per sponsor request. Study drugs are to be stored at room temperature.

6.3 Method of Assignment to Treatment

Approximately 256 patients will be randomized to either one of two treatment groups in a 1:1 ratio. A randomization list in blocks of four will be generated centrally by the sponsor/or CRO for each site.

Approximately 13 blocks, i.e. enough study medication for a maximum of 52 patients will be sent to each study site prior to patient enrollment. A treatment vial, consisting of one vial of either cetirizine or diphenhydramine, based on the treatment assignment of the centralized randomization schedule, will be packaged for each randomization number and labeled by the randomization number, using a blinded label to cover the product name. A list will contain assignment of sequential numbers to one of the two treatment groups. The original randomization list will be kept secured until the study blind is broken. At the investigational site, each randomized subject will be assigned a subject identifier number. This identifier number ("Subject Number" or "Subject Identification Number") will be used on all subject documentation. Subject Numbers will be assigned in ascending sequential order. The Subject Number will consist of two digits (site number) followed by three digits (subject number), e.g. 02-009 (the 9th patient enrolled at site #2).

The randomization number (Treatment Number) for each subject with its Subject Number will be allocated at baseline and entered in the source document or eCRF, after verifying the inclusion and exclusion criteria.

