| MOP | Manual of Procedures |
| N | Number (typically refers to subjects) |
| NCI | National Cancer Institute, NIH |
| NDA | New Drug Application |
| NEJM | New England Journal of Medicine |
| NI | Non-inferiority |
| NIAID | National Institute of Allergy and Infectious Diseases, NIH |
| NIH | National Institutes of Health |
| OCRA | Office of Clinical Research Affairs, DMID, NIAID, NIH |
| OHRP | Office for Human Research Protections |
| OHSR | Office for Human Subjects Research |
| ORA | Office of Regulatory Affairs, DMID, NIAID, NIH |
| PHI | Protected Health Information |
| PI | Principal Investigator |
| PK | Pharmacokinetics |
| QA | Quality Assurance |
| QC | Quality Control |
| SAP | Statistical Analysis Plan |
| SAE | Serious Adverse Event/Serious Adverse Experience |
| SD | Standard Deviation |
| SMC | Safety Monitoring Committee |
| SOP | Standard Operating Procedure |
| T _{max} | Time of maximum measured plasma concentration; if it occurs at more than one time point, T _{max} is defined as the first time point with this value |
| WHO | World Health Organization |

PRINCIPAL INVESTIGATOR'S ACKNOWLEDGEMENT

I have read and understand this protocol, agree to conduct the study as outlined herein, and provide the necessary assurances that this study will be conducted according to all stipulations of the protocol, complying with the obligations and requirements of clinical investigators and all other requirements listed in 21 CFR part 312 and all applicable local, state, and federal regulations and ICH guidelines.

Principal Investigator Signature _____

Principal Investigator Name (print) _____

Date _____

Name of Investigational Site _____

1. Protocol Summary

Title:

A Phase III, multi-center, double blind, randomized, active controlled clinical trial to evaluate the Non-Inferiority comparing Cetirizine Injection 10 mg to Diphenhydramine Injection, 50 mg, for the treatment of acute urticaria.

Phase:

Phase III

Population:

Males or females aged 18 years and older, with acute urticaria requiring treatment in Emergency Departments, hospitals, Urgent Care Centers and Allergy Clinics will be included in this study.

Number of Patients and Number of Sites:

Approximately 256 patients, and approximately 20 sites

Study Duration:

Approximately 48 hours.

Study Medications:Investigational Product:

Cetirizine injection, 10 mg/mL – a single 1 mL injection via intravenous slow push (~2 minutes)

Comparator:

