The management of acute urticaria in the ED is usually not dependent on the underlying etiology. Most cases of acute urticaria respond to pharmacotherapy, with antihistamines being first-line treatment⁽⁷⁾. To provide rapid relief of the symptoms and associated pruritus, the parenteral route is preferred, but the only antihistamine available for intravenous administration is diphenhydramine injection. Consequently, during the US National Hospital Ambulatory Medical Care Survey period between December 2008 and December 2009, diphenhydramine was used over 4 million times during patient visits to the ED⁽³⁾. Unfortunately, diphenhydramine (a short acting antihistamine) causes sedation, impairs mental performance, and results in unwanted anticholinergic effects (e.g.: urinary retention, dry mouth/eyes, *etc.*) in a large percentage of patients^(8,9,10,11) all of which complicate patient management and ED discharge. In contrast, cetirizine, a second generation antihistamine, is associated with a lower rate of sedation, a 24-hour duration of action, and is devoid of anticholinergic effects^(10,11,12,13) and other sides effects associated with diphenhydramine.

Development work for cetirizine injection 10 mg/mL was initiated by JDP in 2009. Several clinical trials have been conducted to date:

- Relative bioavailability of cetirizine injection has been investigated in the pharmacokinetics & tolerability study (study # CTN-P0-741) via IV and IM, against the oral tablet of cetirizine. This study was greatly successful. It demonstrated that the AUCs between cetirizine tablet (Zyrtec) and the injection are equivalent, and C_{max} of the cetirizine injection is about 3.5 times of that of the tablet. In addition, JDP's Cetirizine injection did not cause significant adverse events.
- A 2nd relative bioavailability study (Study # CTN-P1-571) on cetirizine injection 10 mg, via IM injection, was also successful without any significant adverse events.

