6.4.3 Randomization and Maintenance of Study Blind

This will be a double-blind study; the investigator, the patient, and any health care professional involved in patient management or outcome assessment will remain blinded. Both cetirizine injection and IV diphenhydramine are presented as a clear aqueous solution in 2 mL amber vials containing 1.0 mL of medication, and having similar physical appearance. A blinded and randomized label created for the study conceals the product label of each vial for both the Investigational drug cetirizine and the comparator diphenhydramine. To further maintain blinding, the randomized medication can be drawn up into a syringe for administration by a staff member who is not involved in patient management or outcome assessment. The healthcare professional involved in patient management and outcome assessment is completely blinded.

Treatment drugs (Investigational drug and Control) will be pre-randomized and blinded at 1:1 ratio by the Sponsor or CRO, according to the randomization schedule (see [Section 6.3](#)), prior to being delivered to each investigational site. At the investigational site, the trial randomization code will remain secure at all times, but may be accessed in the event of an emergency.

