6.4.4 Breaking the Study Blind

In order to preserve the blinding of the study, site personnel will not have access to the randomization code and treatment assignments before data base lock. Study blinding may only be broken if the identity of the study drug is considered vital for the clinical management of the subject.

Since this is an acute care study it is impractical to notify the Sponsor and Medical Monitor prior to breaking the blind for a patient should it be necessary. However, all emergency code breaks must be reported to the Sponsor, CRO, the Medical Monitor and/or the Project Manager in a timely fashion. The time, date, the reason and who broke the blind, must be documented in the source documents and/or will be captured in the eCRF.

If the investigator, patient, or health care professional performing the assessments, is unblinded for whatever reason, the patient will be included in all analyses of the study results, but a replacement patient will be recruited by the center. No assigned Subject ID Numbers will be reused for any subjects.

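### A single fixed block size of four per site is disclosed to every investigator while sedation is expected to differ by arm, so upcoming assignments can be guessed better than chance

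*Protocol*

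**What the plan says.** Protocol section 6.3: "Approximately 256 patients will be randomized to either one of two treatment groups in a 1:1 ratio". On the list itself: "A randomization list in blocks of four will be generated centrally by the sponsor/or CRO for each site". The size can also be read from the supply statement: "Approximately 13 blocks, i.e. enough study medication for a maximum of 52 patients will be sent to each study site prior to patient enrollment". "Subject Numbers will be assigned in ascending sequential order", and the randomization number is allocated at baseline once eligibility has been verified. Section 11.3.1 has each investigator read and sign the protocol. Neither the protocol nor the SAP mentions varying block sizes or keeping the size from sites.

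On clues to treatment, protocol section 2 says diphenhydramine "causes sedation, impairs mental performance, and results in unwanted anticholinergic effects" in a large share of patients, describes a lower sedation rate with cetirizine, and reports lower sedation with cetirizine in the pilot study. No rates are given. Under section 4, site staff record the patient's sedation rating at 1 and/or 2 hours and at readiness for discharge.

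On access to the code, section 6.4.3 says that at the site "the trial randomization code will remain secure at all times, but may be accessed in the event of an emergency". Section 6.4.4 says "site personnel will not have access to the randomization code and treatment assignments before data base lock", and then allows the blind to be broken without prior notice to the sponsor when knowing the drug is vital to the patient's care.

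**The concern.** In a block of four at 1:1, the fourth assignment follows from the first three, and if the first two are alike the last two follow. Anyone who knows the block size and suspects the earlier arms can predict part of the sequence. Covered labels and similar vials do not hide a drug effect that staff see and record.

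Eligibility leaves room for judgement: whether the patient needs an antihistamine (inclusion 1), whether either injection might be poorly tolerated (exclusion 3), and general suitability (exclusion 14). A prediction made before the randomization number is allocated could influence whom staff approach or exclude. The arms could then differ in expected severity or in susceptibility to sedation. That would affect the patient-rated 2-hour pruritus change (D2), the sedation scores and the time to readiness for discharge, which depends on the investigator's judgement and on sedation. SAP section 9.4 plans no covariates for the primary analysis. The centre term in section 9.7 does not correct for selection within a centre.

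**Working it through.** **Inputs from the documents.** Blocks of four, 1:1, by site (6.3). The Protocol Summary gives "Approximately 256 patients, and approximately 20 sites", so 256/20 = 12.8, or about 13 patients per site. SAP sections 2 and 9.7 give 254 subjects and 22 centres, so 254/22 = 11.5.

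**Input not in the documents.** r is the probability that staff correctly recognise an earlier patient's arm. It is assumed equal in both arms and varied below.

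**The plan's own figure.** 13 blocks × 4 = 52 patients per site, which agrees with 6.3.

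**Ceiling (r = 1).** A 2+2 block has six equally likely orders.
- Probability that the assignment is certain, by position: 0, 0, 1/3, 1. Sum 4/3; divided by 4 = 33.3%. For 256 patients, 256/3 ≈ 85.
- Probability of a correct best guess, by position: 1/2, 2/3, 2/3, 1. Sum 17/6; divided by 4 = 70.8%.
- At 13 patients (three full blocks plus one patient): certain (3 × 4/3)/13 = 4/13 = 30.8%; correct (3 × 17/6 + 1/2)/13 = 9/13 = 69.2%.
- At 11 patients (two full blocks plus three patients): certain (2 × 4/3 + 1/3)/11 = 3/11 = 27.3%.

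**Partial recognition (r < 1).** The best guess is correct with probability 1/2 at position 1, 1/2 + (2r − 1)/6 at positions 2 and 3, and r² + 2r(1 − r)² at position 4. At 13 patients the average is (3 × block sum + 1/2)/13.
- r = 0.9: 0.500 + 2 × 0.633 + 0.828 = 2.595; full blocks 64.9%; 13 patients 63.7%.
- r = 0.8: 0.500 + 2 × 0.600 + 0.704 = 2.404; full blocks 60.1%; 13 patients 59.3%.
- r = 0.7: 0.500 + 2 × 0.567 + 0.616 = 2.249; full blocks 56.2%; 13 patients 55.8%.

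For any r below 1 no assignment is certain. In full blocks, the share predictable with at least 90% probability is 2% at r = 0.9 and 0% at r = 0.8. Weaker contrasts give less: with sedation in 60% on diphenhydramine and 30% on cetirizine (assumed), correct guesses are 54.6%; with 50% and 30%, 53.1%. Chance is 50%.

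**Effect of varying sizes.** Simulation with 13 patients per site and sizes drawn with equal probability. The guesser is allowed to know the set of sizes but not the block boundaries.

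| Recognition r | Fixed 4 | Sizes 4, 6 | Sizes 4, 6, 8 |
|---|---|---|---|
| 1.0, certain | 30.8% | about 6% | about 2% |
| 1.0, correct | 69.2% | 67.3% | 66.0% |
| 0.9, correct | 63.7% | 61.2% | 60.1% |
| 0.8, correct | 59.3% | 57.4% | 56.6% |
| 0.7, correct | 55.8% | 54.6% | 54.1% |

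Correct guesses fall by between 1.2 points (55.8 − 54.6) and 3.6 points (63.7 − 60.1).

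**The case against.** The strongest reply is that nothing in the documents says sedation unmasks the individual patient. A reader might infer that diphenhydramine will reveal itself and that a third of assignments will therefore be known before enrolment. The documents do not support this. They describe a difference in group rates, with sedation on cetirizine lower but not said to be absent, and the one-third figure needs every earlier assignment in the block to be recognised without error. This part of the reply stands.

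A reader might also infer that sites hold the whole list, so that one emergency opening exposes every assignment. That is conjecture. Section 6.3 has the list generated centrally and the original kept secured, vials are packaged singly by randomization number, and section 6.4.4 speaks of breaking the blind for one patient, with documentation and reporting. What remains is a conflict of wording between 6.4.3 and 6.4.4, and neither section says how much a break reveals.

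The safeguards in 6.4.3 (similar vials, covered labels, blinded assessors) are real, but they do not hide a drug effect, and the separate person who draws up the dose is optional. Allocating the number after eligibility is verified does not stop a prediction made beforehand.

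Finally, varying the block size barely reduces guessing, and no resulting shift in D2 has been shown. Both statements are correct. They limit the weight of the point but do not justify publishing the block size to the staff who enrol.

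**Conclusion.** The point holds in a limited form. A fixed block size of four is disclosed to the people who enrol, an arm-related sign is visible to them, and nothing in the plan offsets the two together. The result is better-than-chance prediction: about 56% to 64% correct at 13 patients per site if r is 0.7 to 0.9, and less if sedation overlaps more between arms. The values of r are assumptions, and the actual degree of predictability cannot be estimated from the documents. The figures of 33% certain and 71% correct (31% and 69% at 13 per site) are ceilings under complete knowledge of earlier assignments. The size and direction of any bias in D2 are not established. This change should be made because it costs almost nothing before enrolment; the documents do not show that the trial's result would be invalid without it. The conflict between 6.4.3 and 6.4.4 needs correcting whatever one assumes about sedation.

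**What to change.** - **Section 6.3, block size.** Replace the fixed block of four with permuted blocks of randomly varying size within site, and keep the sizes only in the restricted sponsor/CRO randomization file.
- **Section 6.3, supply.** State the supply per site as a number of vials and drop the count of blocks.
- **Sections 6.4.3 and 6.4.4.** Reconcile them to say that site staff hold no list and that an emergency code break reveals one patient's assignment only, for example through one sealed or electronic code per kit.

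The cost is a new list before enrolment, revised protocol wording, slightly larger possible imbalance within a site and a few spare vials. No extra patients are needed and the primary analysis does not change. Because varying sizes removes most of the certainty but little of the guessing, the code-break wording deserves at least equal care.

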6.4 Control Product and Study Medication

- *Investigational Product:* cetirizine injection, a single 1.0 mL injection (10 mg/mL) given by slow intravenous push (~2 minutes).
- *Control Product:* IV diphenhydramine, a single 1.0 mL injection (50 mg/mL) given by slow intravenous push (~2 minutes).

6.4.1 Rationale for Using Diphenhydramine as the Control Product

IV diphenhydramine is the only antihistamine injection available for the treatment of acute urticaria. [REDACTED]

CCI [REDACTED] The approved indication for IV diphenhydramine is as follows:

For amelioration of allergic reactions to blood or plasma, in anaphylaxis as an adjunct to epinephrine and other standard measures after the acute symptoms have been controlled, and for other uncomplicated allergic conditions of the immediate type when oral therapy is impossible or contraindicated⁽¹⁴⁾.

6.4.2 Rationale for Selection of the Dose of cetirizine injection

The recommended dose of oral cetirizine is 10 mg (Zyrtec®/Reactine® Prescribing Information). This dose has been shown to strongly inhibit the wheal and flare caused by the intradermal injection of histamine. The onset of this activity after a single 10 mg oral dose occurs within one hour in 95% of subjects.

CCI [REDACTED]

Although direct comparisons between IV diphenhydramine and IV cetirizine in the medical literature are lacking, the generally recommended doses to manage acute allergic reactions are 50 mg and 10 mg, respectively⁽¹¹⁾. Furthermore, cetirizine, 10 mg oral tablet is commonly used to treat acute urticaria by allergists^(11,12). Cetirizine 10 mg is also the Reference Listed Drug (RLD) dose specified by the FDA.

JDP conducted its direct comparison study between IV cetirizine 10 mg and IV diphenhydramine 50 mg in a pilot phase III clinical trial (ETTAU-02) with a similar study design as the current study (ETTAU-03) as a preparation for the current study to streamline recruiting, IRB process, and IND, etc. ETTAU-02 demonstrated a similar efficacy in acute urticaria symptom score reductions while in the treatment centers between the two treatment groups (Cetirizine injection 10 mg and diphenhydramine injection), demonstrated an earlier patient discharge time from treatment centers with the cetirizine group than the diphenhydramine group, and also demonstrated a lower symptom recurrence rate with the cetirizine group within ~24 hours after discharge than with the diphenhydramine group, etc. The 10 mg Cetirizine dosage in an injection form was shown to be similarly effective as diphenhydramine injection in the pilot phase III study, and thus was selected for the current study.

6.4.3 Randomization and Maintenance of Study Blind

This will be a double-blind study; the investigator, the patient, and any health care professional involved in patient management or outcome assessment will remain blinded. Both cetirizine injection and IV diphenhydramine are presented as a clear aqueous solution in 2 mL amber vials containing 1.0 mL of medication, and having similar physical appearance. A blinded and randomized label created for the study conceals the product label of each vial for both the Investigational drug cetirizine and the comparator diphenhydramine. To further maintain blinding, the randomized medication can be drawn up into a syringe for administration by a staff member who is not involved in patient management or outcome assessment. The healthcare professional involved in patient management and outcome assessment is completely blinded.

Treatment drugs (Investigational drug and Control) will be pre-randomized and blinded at 1:1 ratio by the Sponsor or CRO, according to the randomization schedule (see [Section 6.3](#)), prior to being delivered to each investigational site. At the investigational site, the trial randomization code will remain secure at all times, but may be accessed in the event of an emergency.

6.4.4 Breaking the Study Blind

In order to preserve the blinding of the study, site personnel will not have access to the randomization code and treatment assignments before data base lock. Study blinding may only be broken if the identity of the study drug is considered vital for the clinical management of the subject.

Since this is an acute care study it is impractical to notify the Sponsor and Medical Monitor prior to breaking the blind for a patient should it be necessary. However, all emergency code breaks must be reported to the Sponsor, CRO, the Medical Monitor and/or the Project Manager in a timely fashion. The time, date, the reason and who broke the blind, must be documented in the source documents and/or will be captured in the eCRF.

If the investigator, patient, or health care professional performing the assessments, is unblinded for whatever reason, the patient will be included in all analyses of the study results, but a replacement patient will be recruited by the center. No assigned Subject ID Numbers will be reused for any subjects.

6.4.5 Concomitant Medications/Rescue Drugs

To ensure optimal patient management, additional medications, e.g. epinephrine, steroids, or etc., may be given during the study if deemed necessary by the investigator/designee. However, if without medical complication, all effort should be made to have the patient complete at least the 1 hour assessments prior to administration of the rescue medication. If rescue medication is needed very shortly after study drug administration (e.g. within ~10 -15min), this indicates that the patient might have anaphylaxis. This patient should be withdrawn from the study, because he/she should have been excluded during screening.

The product label of the rescue drugs should be followed to determine the appropriate dose.

The identity, dose, frequency and route of administration of all medications being taken prior to study enrolment will be recorded, as well as all concomitant medications administered during the study (rescue drug).

6.5 *Clinical and Safety Evaluations*

Study procedures and their timing are summarized in the Study Schedule, Protocol [Attachment A](#). All subjects who received at least one dose of study medication will be included in all analyses and safety analyses.

7. Clinical/Efficacy Outcome and Measures

7.1 *Primary Clinical Efficacy Measure*

The primary clinical efficacy outcome measure is the 2-hour patient rated Pruritus Severity Score Reduction/Change from Baseline (**D2**) as defined under [Attachment B](#), comparing between the two treatment groups.

7.2 *Key Secondary Clinical/Efficacy Measures*

The following key secondary clinical or efficacy measures will be assessed for each patient:

- 1) The need to return to treatment center after study discharge (i.e. 2nd visit within approximately ~24 hours after discharge)
- 2) Time spent at the treating center (time from treatment administration to Readiness for discharge)

7.3 *Other Clinical/Efficacy Measures*

The following other clinical or efficacy measures will be assessed for each patient:

- 1) Pruritus treatment success (% of patients), defined as a patient who had the Pruritus Severity Score Reduction of at least 1 unit for the 2-hour patient rated Pruritus Severity score from Baseline (**D2**) as defined under [Attachment B](#), comparing between the two treatment groups.
- 2) Patient rated pruritus severity scores reduction/change from baseline (D1 & D3) at 1 hour and at "time of discharge"
- 3) Sedation Scores, at baseline, 1hr, and/or 2hr, and/or Readiness for Discharge (B2)
- 4) Physician rated Extent of Urticaria/Erythema Scores and their reduction/change from baseline at 1 hour, 2 hours and "time of discharge" (C1, C2, C3).
- 5) Use of rescue medication, e.g. epinephrine, bronchodilators, steroids, etc., and the reasons for the use of rescue drugs
- 6) "Effectively treated" based on investigator's opinion of Yes or No.
- 7) Symptom recurrence and additional symptom occurrence within ~24 - 48 hours after patient discharge from treatment centers.
- 8) The need for prescribed medication within ~24-48 hours after discharge.
- 9) The need for additional medication, including any over-the-counter medications, within ~24 -48 hours after discharge.

10) Ability of returning to normal activity after discharge

8. Safety Evaluations

The safety population is defined as all patients who received study medication. Investigators are responsible for monitoring the safety of patients who are participating in this study and for alerting the Sponsor of any event that seems unusual, even if this event may be considered as an unanticipated benefit to the patient. The investigator is responsible for the appropriate medical care of patients during the study.

The investigator remains responsible for following through an appropriate health care option for adverse events that are serious or that caused the patient to discontinue before completing the study. The patient should be followed until the event is resolved or explained. Frequency of follow-up is left to the discretion of the investigator.

In this study, safety will be evaluated by recording any adverse events for up to 28 days following treatments and by monitoring vital signs at planned intervals from admission into the treating facility until readiness for discharge.

